# 5.2.2. Analyses for Continuous Data

#### 5.2.2.1. Geometric Means

and OPA, and colors and open a

#### 5.2.2.3. Geometric Mean Ratios

#### 5.2.2.4. Reverse Cumulative Distribution Curves

Empirical reverse cumulative distribution curves (RCDCs) will be presented graphically by plotting the proportion of participants with the GBS6 serotype-specific antibody level equal to or exceeding the specified antibody level vs the indicated antibody level for each serotype separately by vaccine group and at a specific blood sampling time point (eg, 1 month after vaccination for nonpregnant women) for participants from different stages. The RCDCs at other time points may be generated. The LLOQ and/or defined threshold values will be marked on the horizontal axis.

# 5.2.2.5. Antibody Response Curves

Antibody response will be graphed for IgG concentrations by vaccine group at blood sampling time points from before vaccination (Day 1) to after vaccination for nonpregnant women with primary vaccination (Stage 1 [3 vaccine groups]), nonpregnant women with a booster vaccination (Stage 1 [1 vaccine group]), and maternal participants (Stage 2 [7 vaccine groups] and Stage 3 [2 vaccine groups]) and similarly for infant participants (Stages 2 and 3) by their mother's vaccine group at birth and postbirth blood sampling time points. The curves will display the geometric mean and 95% CI at each of the time points with a line connecting the geometric means for each vaccine group across time.

Antibody response will also be graphed for OPA titers by vaccine group at blood sampling time points from before vaccination (Day 1) to after vaccination for maternal participants (Stage 2 [7 vaccine groups] and Stage 3 [2 vaccine groups]) and similarly for infant participants (Stages 2 and 3) by their mother's vaccine group at birth and postbirth blood sampling time points. The curves will display the geometric mean and 95% CI at each of the time points with a line connecting the geometric means for each vaccine group across time.

### 5.2.3. Other Analyses

A separate mixed-effects model with repeated measures (MMRM) for maternal and infant participants will be utilized to assess the effects of regressors/covariates, such as vaccine group (maternal vaccine group for infant participants), visit (blood sampling time point), baseline or at-birth GBS6 serotype-specific IgG antibody level, sex (male, female, or undifferentiated as appropriate), age at vaccination (years), delivery outcome (preterm or full-term),

[figure not shown]
on the associated GBS6 serotype-specific postvaccination or postdelivery IgG antibody levels. Details regarding the specific model used for maternal and infant participants are provided in Section 6.3.3.1 and Section 6.3.4.1, respectively. An unstructured covariance matrix will be used to account for intraparticipant correlation. In case the model does not converge, other covariance structures (eg, autoregressive, compound symmetry) will be explored. The baseline and postvaccination IgG antibody levels will be transformed into logarithmic scale for analysis.

# 5.3. Methods to Manage Missing Data

### 5.3.1. Immunogenicity Data

Values recorded as insufficient sera (QNS), indeterminate results, or "Not Done" will be set to missing. No imputation will be done for these missing values.

The GBS6 IgG, and OPA antibody levels above LLOQ are considered accurate. Values below the LLOQ or denoted as below the limit of quantitation (BLQ) will be set to 0.5 × LLOQ.

The GBS6 IgG antibody levels will be standardized as current quantitated values × correction factor. The LLOQ values will be standardized as standardized LLOQ = LLOQ × correction factor. The correction factors are set as follows: Ia, 0.46628125; Ib, 0.463392157; II, 1.451696809; III, 0.727236264; IV, 0.686258373; and V, 0.236850746. The standardized quantitated values will be reported for all analyses.

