In Amendment 5, Stage 1 booster participants (nonpregnant women) will return for an additional blood draw at Visit 10, which will take place approximately 14 to 184 days after Visit 9. This additional serum will further support the development of a universal GBS vaccine reference standard assay.

In Amendment 6, an additional 200 maternal participants will be added to Stage 3. These participants will be recruited at sites in the US. The data from these participants will contribute to the safety database to support the initiation of the Phase 3 program. These data will also enable an evaluation and comparison of GBS6 immune responses and placental antibody transfer efficiency between maternal/infant pairs in the US and South Africa. Furthermore, OPA analysis has been removed as an exploratory endpoint for Stage 1, Stage 2, and Stage 3 maternal and infant participants. It has also been removed as a secondary endpoint for Stage 1 participants. This is being removed because data from the second and third interim analyses demonstrated robust immune responses, as measured by serotype-specific IgG and functional antibody response for serotype-specific OPA after GBS6 vaccination. These data support the use of anti-GBS capsular IgG levels to evaluate GBS6 vaccine protection against invasive GBS disease. However, the lower limits of quantitation (LLOQs) for serotype-specific OPAs were high, indicating that the OPA assays are not sensitive enough compared to IgG, and thus rendering the OPA assay unsuitable for measuring vaccine protection.

In Amendment 7, there will be a revision of the infant blood draw schedule to remove blood draws at the 18-week postdelivery and 12-month postdelivery visits for infants born to maternal participants enrolled in the US and the UK Stage 3 cohort. The infant blood draws at these 2 visits are for the exploratory immunogenicity objective to describe immune responses to diphtheria and 13-valent pneumococcal conjugate vaccine administered to infant participants delivered to maternal participants vaccinated with GBS6, and are aligned with the South African pediatric immunization schedule. The pediatric immunization schedules in the US and the UK differ and are not aligned with the 18-week postdelivery and 12-month postdelivery study visits. This exploratory analysis will continue to be conducted in Stage 2 and Stage 3 infants born to maternal participants enrolled from South Africa as originally planned.

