10.2.2. Analysis of Immunogenicity Endpoints

Immunogenicity endpoints are secondary or exploratory in the study as listed in Section 3.2 and Section 3.3. Descriptive summary statistics will be provided for all immunogenicity endpoints. No formal between-group comparison will be made.

Descriptive evaluations include GBS6 serotype-specific IgG GMCs and OPA GMTs measured at prespecified time points and will be summarized by vaccine group.

GBS6 serotype-specific IgG concentrations will be logarithmically transformed for analysis. For each serotype, GMCs will be calculated at all blood draw visits. Two (2)-sided 95% confidence intervals (CIs) for the GMCs will be constructed by back transformation of the CIs for the mean of the logarithmically transformed assay results computed using Student's t distribution.

OPA GMTs and the corresponding 2-sided 95% CIs for the GBS6 serotype-specific OPA titers will be computed using similar methods to those for IgG concentrations.

The proportions of participants achieving defined GBS6 serotype-specific IgG concentrations and OPA titers will be summarized descriptively at prespecified time points as counts and percentages with 2-sided 95% exact CIs by vaccine group.

All of the binary endpoints will be descriptively summarized with 2-sided exact 95% CIs using the Clopper-Pearson method.

Reverse cumulative distribution curves (RCDCs) for combination of prespecified time points and vaccine groups will be generated for each GBS6 serotype. Additionally, antibody response line plot of geometric means and the associated 95% CIs will be presented at each analysis time point by vaccine group and serotype.

Detailed analyses of all the immunogenicity endpoints including additional exploratory analyses and graphical displays will be described in the SAP.

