## 3.2.2. Secondary Endpoints: Maternal Participants (Stages 2 and 3)

- GBS6 serotype-specific IgG GMCs measured at 2 weeks and 1 month after vaccination and at delivery in maternal participants.
- GBS6 serotype-specific opsonophagocytic activity (OPA) geometric mean titers (GMTs) measured 1 month after vaccination and at delivery in maternal participants.

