## 3.2.3. Secondary Endpoints: Infant Participants (Stages 2 and 3)

- GBS6 serotype-specific IgG GMCs in infant participants measured at birth.
- GBS6 serotype-specific OPA GMTs in infant participants measured at birth.

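### OPA titres below the LLOQ are all set to half the LLOQ, with no limit on how many; where about half or more of a group is below it, the secondary OPA GMT and its CI can mislead

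*SAP*

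**What the plan says.** SAP 5.3.1 states that "The GBS6 IgG, and OPA antibody levels above LLOQ are considered accurate", and for the rest: "Values below the LLOQ or denoted as below the limit of quantitation (BLQ) will be set to 0.5 × LLOQ". The legible text sets no cap on the share replaced. It does not ask for that share to be reported and plans no censored-data or sensitivity analysis.

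Protocol 2.2.5, reporting on the second and third interim analyses, says that "the lower limits of quantitation (LLOQs) for serotype-specific OPAs were high, indicating that the OPA assays are not sensitive enough compared to IgG". Protocol Amendment 6 dropped the exploratory OPA endpoints and the Stage 1 secondary one. Two secondary OPA endpoints remain in Stages 2 and 3:

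- mothers (SAP 3.2.2): "GBS6 serotype-specific opsonophagocytic activity (OPA) geometric mean titers (GMTs) measured 1 month after vaccination and at delivery in maternal participants"
- infants (SAP 3.2.3): "GBS6 serotype-specific OPA GMTs in infant participants measured at birth"

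Protocol 10.2.2 builds IgG CIs from Student's t on the log scale, back-transformed, and treats OPA in a similar way. The same section adds: "The proportions of participants achieving defined GBS6 serotype-specific IgG concentrations and OPA titers will be summarized descriptively". SAP 6.2.2.2 and 6.2.3.2 also plan OPA reverse cumulative distribution curves (RCDCs), and SAP 5.2.2.4 says that the LLOQ and/or a threshold will be marked on them.

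**The concern.** A t interval treats each substituted constant as if it had been measured. When many values share one constant, the mean is pulled towards half the LLOQ, and the SD usually shrinks because the spread below the limit has vanished. The interval then sits in the wrong place and looks too precise. In the extreme, a group entirely below the LLOQ has a GMT of exactly half the LLOQ and a CI of zero width.

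SAP 5.1.1 takes an estimation approach, so the GMT and its CI are the result for these endpoints. They enter the fourth interim analysis, which is meant to support development decisions and possible regulatory discussions, and then the clinical study report. Having reported high OPA LLOQs, the plan would be expected to say what happens when many titres fall below them.

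**Working it through.** The plan gives no figure for OPA precision, so there is nothing to reproduce first.

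**Inputs from the documents.** Substituted value 0.5 × LLOQ (SAP 5.3.1). Two-sided 95% t interval on the log scale (Protocol 10.2.2). Groups of 40 per GBS6 arm in Stage 2 and 108 per arm in Stage 3 (Protocol 10.1; SAP Table 2, based on Protocol Amendment 7, has 98 per arm in Stage 3).

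**Assumed, because the documents do not give them.** Log-normal titres; share q below the LLOQ from 10% to 90%; log10 SD of 0.3, 0.5, 0.7 and 1.0, which on the natural-log scale is σ = 0.7, 1.15, 1.6 and 2.3.

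**Bias.** Put the LLOQ at 0 on the natural-log scale and let z = Φ⁻¹(q), so the true mean is μ = −zσ. After substitution the expected mean is μ(1 − q) + σφ(z) − q ln 2. Hence

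bias = σ[φ(z) + qz] − q ln 2, and GMT ÷ true GMT = exp(bias).

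Example, q = 50%, σ = 1.6: 1.6 × 0.399 − 0.347 = 0.292, and exp(0.292) = 1.34.

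GMT ÷ true GMT:

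| log10 SD | 10% | 25% | 50% | 70% | 90% |
|---|---|---|---|---|---|
| 0.3 | 0.96 | 0.93 | 0.93 | 1.02 | 1.36 |
| 0.5 | 0.99 | 1.00 | 1.12 | 1.40 | 2.47 |
| 0.7 | 1.01 | 1.07 | 1.34 | 1.93 | 4.49 |
| 1.0 | 1.04 | 1.19 | 1.77 | 3.19 | 11.4 |

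At q = 20%, φ(z) + qz = 0.112 and q ln 2 = 0.139. The ratio then runs from exp(0.7 × 0.112 − 0.139) = 0.94 to exp(2.3 × 0.112 − 0.139) = 1.13.

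**SD.** At log10 SD 0.7 the substituted data show 0.75, 0.56 and 0.30 of the true SD at 50%, 70% and 90%. At log10 SD 0.3 with 25% below, the SD is overstated by about 10%.

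**Coverage of the nominal 95% t interval** (20,000 simulated samples per cell), at log10 SD 0.5 / 0.7 / 1.0:

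| Share below LLOQ | n = 40 | n = 108 |
|---|---|---|
| 10% | 95 / 95 / 95% | 95 / 95 / 94% |
| 25% | 95 / 94 / 93% | 95 / 93 / 87% |
| 50% | 91 / 72 / 39% | 79 / 27 / 2% |
| 70% | 10 / 0 / 0% | 0 / 0 / 0% |

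At log10 SD 0.4 and 50% below, the ratio is 1.02 and coverage is 95% (n = 40) and 94.5% (n = 108).

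**Two groups read side by side.** With 10% below in one group and 70% in the other, the ratio of GMTs shrinks to 0.99 ÷ 1.40 = 0.70 of its true value at log10 SD 0.5, 0.52 at 0.7 and 0.33 at 1.0.

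**Alternative.** A left-censored normal likelihood on the log scale, for 25% to 70% below and log10 SD 0.5 to 1.0, gave median GMT ÷ true GMT of 0.97 to 1.12 and coverage of 92 to 96%. It was simulated under its own log-normal assumption. It also weakens under very heavy censoring: at n = 40, log10 SD 0.7 and 90% below, coverage was roughly 82 to 85% and some samples (about 8%) gave no usable estimate.

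**The case against.** The strongest reply is that nothing shows that many OPA titres are below the LLOQ. The protocol calls the LLOQs high in comparison with IgG, and the same paragraph reports robust OPA responses at interim. That stands: the harm is conditional on a share and an SD that are not given, and with a small SD it can be negligible or change sign.

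Second, little hangs on these numbers. All analyses are descriptive, no OPA vaccine-to-placebo ratio is legible, and the sponsor already regards OPA as unsuitable for measuring protection and relies on IgG. This limits the consequence, but a published secondary GMT should still carry a usable CI.

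Third, the RCDCs and the protocol's OPA proportions already show part of the problem. That is true where the LLOQ itself is marked, but neither display corrects the GMT or its CI. The legible infant OPA rows of SAP Table 11 list no proportion.

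Fourth, SAP 5.2.2.1 on geometric means and parts of Table 11 are unreadable, so further OPA handling cannot be excluded.

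A reader might go further and infer that infants at birth are the worst case, or that dose selection is at risk. The documents support neither. Infants of vaccinated mothers may carry transferred antibody. SAP 5.2 already names the Stage 3 formulation, so that choice has been made.

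**Conclusion.** The point holds in conditional form. The substitution rule has no upper limit, and the protocol itself reports high OPA LLOQs. If about half or more of a group's titres are below the LLOQ, the half-LLOQ GMT is usually too high: 1.12 to 1.77 times at 50%, and 1.40 to 3.19 times at 70%, for log10 SD 0.5 to 1.0. CI coverage is then 2 to 91% at 50% and at most 10% at 70%. Placebo groups and weak serotypes are the most plausible places.

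At about 20% or less below the LLOQ, the GMT is within about 13% of the truth over the SDs examined. All of this rests on log-normal titres and on assumed shares and SDs. It would be wrong to infer that the OPA GMTs in this trial are in fact badly biased: the documents do not give what is needed to size the error. The sponsor can read the share directly from its interim data.

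**What to change.** Amend SAP 5.3.1 and the OPA reporting sections (6.2.2.2 and 6.2.3.2) as follows:

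1. Beside every OPA GMT, report n and % below the LLOQ, or equivalently the % at or above it with its exact CI.
2. For any serotype and time point where some group exceeds a prespecified share (for example 30%), add a left-censored log-normal likelihood GMT and CI for all groups alike, as a supplementary estimate. Keep the half-LLOQ GMT for comparability. Applying this to every group avoids mixing two estimators in one comparison.
3. Where a group exceeds a prespecified upper share (for example 80%), or has too few quantified values, give no GMT CI. Rely there on the proportion at or above the LLOQ and on the RCDC with the LLOQ marked.

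The two thresholds are illustrative; what matters is fixing them before the remaining analyses. The cost is SAP wording, a standard procedure and a few more table columns, with no new data. The supplementary estimate relies on log-normality below the limit, which the data cannot confirm.

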#### 5.3.2. Safety Data

Standard algorithms on handling missing AE dates and missing AE severity will be applied as described in the Vaccine Statistics Rulebook.

#### 5.3.2.1. Reactogenicity Data

For derived variables based on reactogenicity data, if any day of the 7-day e-diary is available, the "any day (Day 1-7)" data will be considered as nonmissing.

The reactogenicity data are collected through the e-diary, which does not allow participants to skip the question. Therefore, for a specific day, as long as the e-diary data are transferred for that day, all of the reactogenicity data for the participant on that day is nonmissing. No missing reactogenicity data will be imputed other than what is described in Section 3.6.2.

#### 6. ANALYSES AND SUMMARIES

- 6.1. Primary Endpoint(s)
- 6.1.1. Primary Endpoint(s): Nonpregnant Women (Stage 1)
- 6.1.1.1. Proportion of Nonpregnant Women Reporting Prompted Local Reactions Within 7 Days Following Administration of the Primary and Booster Investigational Product

The analysis will be performed for the primary and booster doses.

Endpoints: Maximum severity during the analysis time interval for pain at the injection site, redness, and swelling.

- Analysis time points: Days 1 through 7.
- Analysis population: Safety population for nonpregnant women (Stage 1).
- Analysis methodology: Descriptive summary statistics.
- Supporting objective: Primary safety objective.

#### Reporting results:

 Raw data: The numerator (n), denominator (N) used for the calculation of proportion, proportion, and associated 2-sided exact 95% CI will be presented for each severity (mild, moderate, severe, and Grade 4) of each local reaction, by vaccine group (3 vaccine groups for primary vaccination and 1 vaccine group for booster vaccination).

Figures: None.

# 6.1.1.2. Proportion of Nonpregnant Women Reporting Prompted Systemic Events Within 7 Days Following Administration of the Primary and Booster Investigational Product

The analysis will be performed for the primary and booster doses.

Endpoints: Maximum severity during the analysis time interval for fever, nausea/vomiting, diarrhea, headache, fatigue/tiredness, muscle pain, and joint pain.

- Analysis time points: Days 1 through 7.
- Analysis population: Safety population for nonpregnant women (Stage 1).
- Analysis methodology: Descriptive summary statistics.
- Supporting objective: Primary safety objective.

 Raw data: The numerator (n), denominator (N) used for the calculation of proportion, proportion, and associated 2-sided exact 95% CI will be presented for each severity (mild, moderate, severe, and Grade 4) of each systemic event, by vaccine group (3 vaccine groups for primary vaccination and 1 vaccine group for booster vaccination).

Figures: None.

# 6.1.1.3. Proportion of Nonpregnant Women Reporting AEs Through 1 Month Following Administration of the Primary and Booster Investigational Product

The analysis will be performed for the primary and booster doses.

Endpoints: AEs experienced by nonpregnant women (Stage 1).

- Analysis time points: Day 1 to 1 month after vaccination.
- Analysis population: Safety population for nonpregnant women (Stage 1).
- Analysis methodology: Descriptive summary statistics.
- Supporting objective: Primary safety objective.

#### Reporting results:

- Raw data: The number of participants with AEs (n), proportion, and associated 2-sided exact 95% CI will be presented for any AEs, SAEs, immediate AEs, severe AEs, related AEs, MAEs, and AEs leading to withdrawal, by vaccine group (3 vaccine groups for primary vaccination and 1 vaccine group for booster vaccination). Additionally, number of participants with AEs (n), proportion, and associated 2-sided exact 95% CI will be presented for any AE, each system organ class (SOC), and each preferred term within SOC, by vaccine group (3 vaccine groups for primary vaccination and 1 vaccine group for booster vaccination).
- Tier 2 AEs: The number of participants with AEs (n), proportion, risk difference, and associated 2-sided exact 95% CI will be presented for each preferred term.

Figures: None.

6.1.1.4. Proportion of Nonpregnant Women Reporting MAEs and SAEs Through 6 Months Following Administration of the Primary Dose and Through Approximately 7 to 12 Months Following Booster Investigational Product

The analysis will be performed for the primary and booster doses.

Endpoints: MAEs and SAEs experienced by nonpregnant women (Stage 1).

- Analysis time points: Day 1 through 6 months after primary vaccination and Day 1 through approximately 7 to 12 months after booster vaccination.
- Analysis population: Safety population for nonpregnant women (Stage 1).
- Analysis methodology: Descriptive summary statistics.
- Supporting objective: Primary safety objective.

• Raw data: The number of participants with AEs (n), proportion, and associated 2-sided exact 95% CI will be presented for any AEs, SAEs, immediate AEs, severe AEs, related AEs, MAEs, and AEs leading to withdrawal, by vaccine group (3 vaccine groups for primary vaccination and 1 vaccine group for booster vaccination). Additionally, number of participants with AEs (n), proportion, and associated 2-sided exact 95% CI will be presented for any AE, each SOC, and each preferred term within SOC, by vaccine group (3 vaccine groups for primary vaccination and 1 vaccine group for booster vaccination), separately for all AEs, SAEs, related AEs, and MAEs.

Figures: None.

6.1.2. Primary Endpoint(s): Maternal Participants (Stages 2 and 3)

6.1.2.1. Proportion of Sentinel-Cohort Maternal Participants (Stage 2 Only) With Clinical Laboratory Abnormalities Following Administration of the Investigational Product at the 2-Week Follow-Up Visit

Endpoint: Abnormalities in safety laboratory parameters are based on the toxicity grading scale for pregnant women provided in Section 3.6.3.

- Analysis time point: Visit 2 (2 weeks after vaccination).
- Analysis population: Safety population for maternal participants (Stage 2 only).
- Analysis methodology: Descriptive summary statistics.
- Supporting objective: Primary safety objective.

### Reporting results:

 Raw data: The n and proportion will be presented for laboratory parameters (eg, hemoglobin, WBC) normal and for each grade (1 through 4), by vaccine group, for sentinel-cohort maternal participants from Stage 2 only.

Figures: None.

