7.2.4. Visit 2 – 2-Week Follow-Up Visit (14-17 Days After Visit 1)

If delivery occurs before this visit, this visit will not be conducted; however, the hematology and chemistry assessments planned to be collected at this visit should be conducted at the delivery visit, if possible. For the other procedures to be conducted at delivery, see Section 7.2.6.

- Ensure that the participant continues to be eligible for the study and meets none of the participant withdrawal criteria as described in Section 7.5.
- Measure vital signs, including weight, oral temperature, sitting blood pressure and pulse rate, and respiratory rate.
- Perform a targeted physical examination, evaluating any clinically significant
 abnormalities based on history and the participant's self-reported symptoms or
 complaints since the last visit. Abnormal results, including those that indicate
 worsening of medical history conditions, must be recorded on source documents
 and the AE CRF (with recording of time relative to vaccination) as appropriate.
- Perform obstetric examination including but not limited to fundal height, fetal heart tones, and fetal movement.
- Collect a blood sample of approximately 15 mL for immunogenicity assessments.
- Stage 2 sentinel cohort only: Obtain a blood sample (approximately 10 mL) for hematology and blood chemistry assessments. The following parameters will be assessed:
 - Hematology: hemoglobin, hematocrit, RBC count, WBC count with differential, and platelets.
 - Blood chemistries: ALT, AST, alkaline phosphatase, total bilirubin, BUN, and creatinine.
 - Retesting of abnormal laboratory parameters will be allowed at the discretion of the investigator if the investigator believes the results to be erroneous.
- Review the participant's e-diary data and collect the e-diary. Collect stop dates of any e-diary events ongoing on the last day that the e-diary was completed and record stop dates in the CRF.
- Complete the participant's source documents.
- Record nonstudy vaccinations and concomitant medications (including antibiotic medications) as described in Section 6.10.3.
- Record AEs as described in Section 8.8 and Section 9.
- The investigator or an authorized designee completes the CRF.

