#### 2.2. Study Design

This is a Phase 1/2, randomized, placebo-controlled, observer-blinded trial to evaluate the safety, tolerability, and immunogenicity of a multivalent GBS6 vaccine in healthy 18- to 40-year-old nonpregnant women as well as pregnant women and their infants. Participants in Stage 2 will be vaccinated between 27 0/7 and 35 6/7 weeks' gestation, and participants in Stage 3 will be vaccinated between 24 0/7 and 35 6/7 weeks' gestation. A total of approximately 622 participants (66 nonpregnant women and 556 maternal participants and their infants) will be enrolled in this study.

## 2.2.1. Stage 1

Nonpregnant women in good health will be screened, enrolled, and randomized in a 1:1:1 ratio (approximately 22 participants enrolled/group) to receive placebo (saline control) or GBS6 (20 µg capsular polysaccharide [CPS]/serotype/dose) with or without aluminum phosphate (AlPO4) (see Table 2).

Stage 1 participants (nonpregnant women) willing and eligible to participate will return to receive a booster dose of GBS6 approximately 2 years after the primary dose of investigational product.

#### 2.2.2. Stage 2

Stage 2 will utilize a sentinel-cohort design, with cohort progression and dose escalation taking place after a safety review (data from each maternal participant through 14 days after vaccination) of the sentinel cohort of participants at each dose level. Pregnant women, once consented, will be referred to as "maternal participants". The first 42 eligible maternal participants at each dose level will compose a sentinel cohort. Starting with the lowest dose level, maternal participants will be randomly assigned (in a 1:1:1 ratio, 14 participants per group) to receive a single dose of GBS6, formulated with or without AlPO4, or placebo (saline control) within the sentinel cohort of a given dose level. Further enrollment will be expanded at each dose level until 78 additional participants are enrolled (expanded cohort).

Approximately 360 maternal participants are planned to be enrolled in Stage 2 (see Table 2).

#### 2.2.3. Stage 3

Approximately 196 additional maternal participants will be enrolled in Stage 3 to receive a single dose/formulation of the selected GBS6 or placebo (saline control) in a 1:1 ratio (see Table 2).

Table 2. Planned Participants: Total and Number in Each Stage and Group

Stage 1 D	ose/Formulation Group a (Nonpregnant Women)		Total (1:1:1)		

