### 3.6.3. Laboratory Data

Laboratory data will be collected for the maternal participants (Stage 2 sentinel cohort) only at screening, at rescreening if applicable, and at Visit 2 (2-week follow-up visit). If abnormal laboratory parameters are reported at screening (Visit 0) or Visit 2 and the investigator believes the results to be erroneous, the abnormal laboratory parameters may be retested. In such cases, only the worst result will be used for summary. The parameters of interest at each visit are listed in Table 7.

Table 7. Laboratory Tests

Hematology	Chemistry
Hemoglobin	BUN and creatinine
Hematocrit	AST, ALT
RBC count	Total bilirubin
Platelet count	Alkaline phosphatase
WBC count	
Total neutrophils (Abs)	
Eosinophils (Abs)	
Monocytes (Abs)	
Basophils (Abs)	
Lymphocytes (Abs)	

Abbreviations: Abs = absolute; ALT = alanine aminotransferase; AST = aspartate aminotransferase; BUN = blood urea nitrogen; RBC = red blood cell; WBC = while blood cell.

The toxicity grading scale in Table 8 for maternal participants will be adapted, as appropriate at a specific time point (eg, based on the pregnancy status at the visit), for grading laboratory test abnormalities. For the grading scale, second trimester is defined as 14 1/7 through 28 0/7 weeks' gestation and third trimester as 28 1/7 weeks' gestation through delivery.

Table 8. Hematology and Blood Chemistry Toxicity Grading Scale for Maternal Participants

	Pregnancy Status	Normal Range	Mild (Grade 1)	Moderate (Grade 2)	Severe (Grade 3)	Grade 4
Female Hb, g/dL	Second trimester	9.7-14.8	9.0-9.6	8.0-8.9	7.0-7.9 or requires a transfusion	<7.0 or life-threatening acute blood loss
	Change from baseline		1.6-2.0	2.1-4.5	4.6-5.0	>5.0
	Third trimester	9.5–15.0	9.0-9.4	8.0-8.9	7.0-7.9 or requires a transfusion	<7.0 or life-threatening acute blood loss
	Change from baseline		1.6-2.0	2.1-4.5	4.6-5.0	>5.0

Table 8. Hematology and Blood Chemistry Toxicity Grading Scale for Maternal Participants

	Pregnancy	Normal	Mild	Moderate	Severe	
	Status	Range	(Grade 1)	(Grade 2)	(Grade 3)	Grade 4
Platelets high, 1000 cell/mm³	Second trimester	155-409	410-499	500-749	750-1000	>1000
	Third trimester	146-429	430-499	500-749	750-1000	>1000
Platelets low, 1000 cell/mm 	Second trimester	155-409	125-154	100-124	25-99	<25
	Third trimester	146-429	125-146	100-124	25-99	<25
WBC high, 1000 cell/mm 	Second trimester	5.6-14.8	>14.8-16.0	>16.0-20.0	>20.0-25.0	>25.0 signs of septic shock

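### SAP Table 8, which grades the primary sentinel laboratory endpoint, is neither mutually exclusive nor exhaustive at Visit 2: one platelet value has two categories, and some bilirubin, neutrophil, hematocrit and RBC values have none

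*SAP*

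**What the plan says.** SAP 6.1.2.1 ties the endpoint to the grading scale: "Abnormalities in safety laboratory parameters are based on the toxicity grading scale for pregnant women provided in Section 3.6.3". The output for each parameter has five possible categories and no others: "The n and proportion will be presented for laboratory parameters (eg, hemoglobin, WBC) normal and for each grade (1 through 4), by vaccine group". It covers the Stage 2 sentinel cohort at Visit 2.

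SAP 3.6.3 supplies two tables. On the first it says "The parameters of interest at each visit are listed in Table 7"; Table 7 includes hematocrit and RBC count. Table 8 gives a normal range and grades by trimester, where "second trimester is defined as 14 1/7 through 28 0/7 weeks' gestation and third trimester as 28 1/7 weeks' gestation through delivery".

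On timing, SAP 2.2 states "Participants in Stage 2 will be vaccinated between 27 0/7 and 35 6/7 weeks' gestation", and Protocol 7.2.4 sets Visit 2 at "14-17 Days After Visit 1".

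Protocol 8.5.3 describes a toxicity scale adapted for pregnant women and refers to the study reference manual (SRM) for detail. The SRM is not among the documents.

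**The concern.** A table that reports each woman as normal or Grade 1 to 4 works only if those categories cover every possible value once. If a value fits two categories or none, the rows do not add to the number tested, and the programmer decides where the woman goes.

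This is a primary safety endpoint in small groups. Women whose screening results fall outside the pregnancy reference range are excluded from the sentinel cohort (Protocol 5.5), so an out-of-range value at Visit 2 is generally new since screening, which is what the endpoint is meant to show. SAP 3.6.3 also keeps only the worst result after a retest, and a value without a grade cannot be ranked against one that has a grade.

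**Working it through.** **Step 1: which rows apply at Visit 2.** Earliest vaccination is at 27 0/7 weeks, or 27 × 7 = 189 days. Adding the minimum of 14 days gives 203 days, or 29 0/7 weeks. The third trimester starts at 28 1/7 weeks, or 28 × 7 + 1 = 197 days. Since 203 is later than 197, third-trimester rows govern every regular Visit 2.

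**Step 2: third-trimester rows, taken literally.** I stepped through values at the precision printed in Table 8.

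| Parameter | Normal | Adjacent grade(s) | Result |
|---|---|---|---|
| Platelets (1000/mm³) | 146-429 | low Grade 1: 125-146 | 146 is in both |
| Bilirubin, normal LFTs (ULN 1.1 mg/dL) | 0.1-1.1 | Grade 1 to 1.5 × ULN; Grade 2 from above 1.6 × ULN | above 1.5 × 1.1 = 1.65 and up to 1.6 × 1.1 = 1.76 mg/dL has no grade (1.7 at one decimal) |
| Neutrophils (1000/mm³) | 3.9-13.1 | low side only, from below 3.9 | above 13.1 has no category |
| Hematocrit, RBC count | none given | none given | no value can be classified |

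The second-trimester rows show that the first two are slips. Platelets there are 155-409 normal and 125-154 Grade 1, with no overlap. Bilirubin Grade 1 ends and Grade 2 begins at 1.5 × ULN, with no gap.

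Other directions without a third-trimester category are hemoglobin above 15.0, BUN below 3, creatinine below 0.4, AST below 4, ALT below 2 and alkaline phosphatase below 38.

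**Step 3: the second-trimester WBC row.** Normal starts at 5.6 and low Grade 1 is below 5.5 down to 3.5, so 5.5 has no category. The third-trimester row starts exactly at its normal limit (5.9). By step 1 this gap does not reach a regular Visit 2. It can matter at screening, or if delivery at or before 28 0/7 weeks replaces Visit 2.

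**Step 4: size.** Each GBS6 sentinel group has 14 women, so one woman is 1/14 = 7.1%. The exact 95% intervals are 0 to 23.2% for 0/14 and 0.2 to 33.9% for 1/14. Placebo pooled over three dose levels is 3 × 14 = 42, where one woman is 2.4%.

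**Not covered.** Monocytes and basophils, whose grades are partly in words; the hemoglobin change-from-baseline rows; and the blank Grade 4 cell for second-trimester bilirubin with normal LFTs, which may be an artefact of PDF extraction.

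**The case against.** The boundary errors are very small: one integer platelet value and one one-decimal bilirubin value, at the normal/Grade 1 and Grade 1/2 borders. The analysis is descriptive, with no decision rule (SAP 5.1.2). The laboratory parts of the stopping rules use Grades 3 and 4 (Protocol 8.7). All of this stands and limits the point.

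A toxicity scale may also deliberately grade one direction only. That is a fair choice, and it means the endpoint should not be recast as any out-of-range value. It still leaves those women without a row. High WBC is graded, but this does not cover high neutrophils: with total WBC 16.0 and neutrophils 13.5, WBC is normal (5.9-16.9) and neutrophils have no category.

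The SRM, or the mock-up tables and programming rules prepared separately (SAP 2), may settle some of this. I cannot rule that out, but SAP 6.1.2.1 makes the SAP's own scale the basis of the endpoint. The sentence in SAP 3.6.3 that lets the scale be adapted, with pregnancy status as its example, gives no rule for these values. The abnormal-result listings in SAP 6.7.3 do not complete the summary table.

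**Conclusion.** The point holds. As printed, Table 8 puts one platelet value in two categories at Visit 2, and leaves a narrow bilirubin band, high neutrophils, several other ungraded directions and two whole parameters with no category. The consequence is a primary safety table whose rows need not add to the number tested, with up to 7.1 percentage points per woman in a group of 14. It concerns normal, Grade 1 and Grade 2 counts and unclassified values only. This rests on the tables as printed and on Visit 2 taking place as scheduled.

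A reader might infer three stronger things that the documents do not support:
- *That the WBC gap distorts the endpoint.* It sits in a row that a regular Visit 2 does not use.
- *That a vaccine effect on neutrophils is being hidden.* Nothing in either document says that raised neutrophils are an expected response.
- *That the number of affected women can be estimated by treating the normal ranges as percentiles.* The documents do not describe them so, and the screening exclusion means these women are not an unselected sample.

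**What to change.** In SAP 3.6.3, reconcile the platelet, bilirubin and WBC boundaries in Table 8 with each row's own normal limit, the matching row for the other trimester, and the source scale and SRM, so that each value falls in exactly one category. The sponsor should confirm the cut-offs from those sources.

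In SAP 6.1.2.1, keep the toxicity-scale endpoint. Add display rows *above range, not graded* and *below range, not graded* for directions without grades. Report hematocrit and RBC count as below, within or above the laboratory's pregnancy reference range, a type of range that the protocol already uses at screening. Categories then add to the number tested.

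The cost is SAP table corrections and a rerun of one table on existing data. The sentinel cohort is unblinded at the second interim analysis (SAP 7.2), and Protocol 1.1 already cites results from that analysis, so label the change as made after unblinding. Counting every out-of-range value as an abnormality would go further: it would alter a primary endpoint definition, and both documents say that a major change of that kind must also appear in a protocol amendment. The display rows avoid this.
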